## **1 BACKGROUND AND STUDY RATIONALE**

### **1.1 Background**

Terminology regarding how to measure the patient and family experience when a child receives medical or surgical care varies and includes patient-reported outcome measures (PROMs), patient-reported experience measures, and patient satisfaction. Preoperative patient education and postoperative patient participation are key components of the multimodal enhanced recovery after surgery (ERAS) protocols, which are gaining force in elective surgical procedures and impact both surgical outcomes and patient-reported outcomes. However, ERAS protocols and standardized care pathways have rarely been adopted in pediatric populations, and there exists a paucity of high-quality literature examining outcomes associated with implementation of enhanced recovery programs (ERPs) in children. Pediatric ERAS implementation has been met with many hurdles, including accounting for physiological differences between adults and children, the divergence of specific disease incidences between adults and children, and bridging the knowledge from adult pathways to pediatric-specific diseases which have no adult analogs. Therefore, specific pediatric preoperative patient/family education and postoperative patient/family participation needs to be developed to achieve reliable pediatric ERAS protocols. Medical procedures are considered especially stressful for children and parents. From over 5 million children that undergo elective surgery in North America each year, almost 75% of them experience considerable anxiety. Child anxiety is associated with many problems beginning with less cooperation with the anesthetic procedure, higher needs for analgesic usage, post-operative pain, slower recovery, delays in hospital discharge, and changes in behavior during the post-operative period. Also, preoperative anxiety can affect children's future interactions with medical personnel representing a long-term consequence. A major risk factor for children's distress is parental anxiety, which is also linked to physical and mental health problems for parents themselves. Based on these findings, different interventions have been studied in an attempt to reduce the burden for families. Audiovisual interventions for parents whose children were undergoing elective surgery had positive effects on both parental and children's preoperative anxiety. However, there has been no study on interventions to reduce parental anxiety during a child's surgical emergency.

Moreover, there has been little research, both in adults and in children, on the applicability and effectiveness of these same ERAS protocols for patients undergoing emergency surgery. Many of the limitations in acute care surgery come from the unpredictability of the timing for surgery and the variability of preoperative care, making it difficult to standardize postoperative care and offer perioperative counseling.

Although there are high numbers of surgical procedures performed in children, the impact on caregivers and families is poorly described. In the context of transitioning to same-day or early post-operative discharges, parents are facing the responsibility of having to care for their child early in the recovery process. This can lead to significant indirect costs associated with loss in productivity at work and at home, and increase caregiver anxiety and caregiver demands. The

magnitude of these indirect costs and loss in productivity has never been measured in a pediatric surgical setting. In reference to the ERAS guidelines, specifically the pillar of preoperative counseling and education, our aim in this research study is to implement an education tool, developed in collaboration with the McGill University Health Center Patient Education Office, for patients and caregivers in both elective and emergency surgical contexts and report its impact on indirect costs and caregiver productivity during the post-operative period. We hypothesize that by providing consistent and accessible information to patients and caregivers we may minimize anxiety, maximize satisfaction, and mitigate caregiver productivity loss during the post-operative recovery period, specifically within 2 weeks of discharge from the hospital.

We aim to examine the impact of a patient education tool in both the emergency and elective surgical settings:

#### 1.1.1 Emergency Surgery - Appendectomies

We have chosen appendectomies for acute appendicitis as the emergency surgical setting given that appendicitis is one of the most common causes of acute abdominal pain, with a lifetime risk of 8.6% in males and 6.7% in females and has the highest incidence in children aged 10-19 years old. Laparoscopic appendectomy performed within the first 24 hours of diagnosis is the standard treatment for acute appendicitis, and hospital admission varies based on whether or not the appendix has perforated, with patients with simple appendicitis going home the same day or the day following operation. Around 25-30% of appendicitis presents with perforation and those patients require a longer hospital admission. At the Montreal Children's Hospital (MCH) we perform approximately 300 appendectomies for acute appendicitis per year.

#### 1.1.2 Elective Surgery – Inguinal and Umbilical Hernias

For the elective surgical setting, we have chosen to target patients with umbilical and inguinal hernias who are booked for elective surgical repairs. Inguinal hernias occur in approximately 3-5% of term infants and 13% of infants born at less than 33 weeks gestational age. Inguinal hernias are commonly repaired to avoid incarceration of the hernia, and at the MCH we perform approximately 240 inguinal hernia repairs per year. Umbilical hernias are also one of the more common pediatric conditions, occurring in approximately 1 in every 6 children. However, they are more likely to close spontaneously and resolve without surgery than inguinal hernias. Nevertheless, some umbilical hernias do cause symptoms and may also fail to regress, thus necessitating surgical repair. At the MCH, we perform approximately 140 umbilical hernia repairs per year.

We hope that by testing the impact of education tools on such a large sample of patients, we will demonstrate an accurate measure of our primary outcome and continue to improve our patient-centered care practices in the realm of pediatric surgery. Furthermore, we believe that this study will serve as further evidence in support of a movement towards ERAS protocols and standardized care pathways in pediatric surgical centers.

## 2 OBJECTIVES, HYPOTHESIS AND STUDY QUESTIONS

### 2.1 Objectives

- Create education tools for patients and caregivers to educate them on the diagnosis, surgical management, and post-operative recovery process for acute appendicitis, umbilical hernias, and inguinal hernias.
- Test whether the education tool reduces parental anxiety and improves satisfaction with care during a child's surgical illness.
- Test whether the education tools impact caregiver productivity loss in the immediate post-operative period, specifically 10-14 days post-discharge.

### 2.2 Hypothesis

We hypothesize that implementing an education tool for patients and caregivers will decrease parental anxiety, improve satisfaction, and mitigate productivity loss among caregivers after hospital discharge.

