## **4 DATA ANALYSIS**

The primary outcome that will be assessed is the loss of parental productivity measured in hours of paid or unpaid work missed due to caring for a child in the post-operative recovery period in caregivers who received the education tool compared to those who did not. Secondary outcomes that will be assessed include: household income (dollar amount) lost due to indirect productivity losses, hours of sleep lost, hours of leisure time lost, number of times that medical assistance is sought in the post-operative period, and need for compensated or non-compensated help at home.

Bivariate analysis will be performed using 2 sample t-tests for dichotomous predictor variables, Fisher's exact test or one-way ANOVA for categorical predictor variables, and Pearson correlation for continuous predictors where appropriate. A p-value of < 0.05 will be deemed statistically significant.

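### The primary outcome has no single start point (surgery or discharge); if it starts at discharge, admission hours drop out and a difference in stay between phases can bias the comparison

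*Combined protocol and SAP*

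**What the plan says.** Three places tie productivity loss to discharge:

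- Section 1.1 expects a benefit "during the post-operative recovery period, specifically within 2 weeks of discharge from the hospital".
- The third objective in Section 2.1 looks at loss "in the immediate post-operative period, specifically 10-14 days post-discharge".
- Section 2.2 expects the tool to "mitigate productivity loss among caregivers after hospital discharge".

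Two places do not. The study question in Section 2.3 names the post-operative period only. Section 4 defines the primary outcome as "loss of parental productivity measured in hours of paid or unpaid work missed due to caring for a child in the post-operative recovery period", with no first or last day. Section 3.3 lists hours of absence from a paid or unpaid job without a recall period.

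On length of stay, Section 1.1.1 says that simple appendicitis goes home on the day of operation or the next day, and adds: "Around 25-30% of appendicitis presents with perforation and those patients require a longer hospital admission". Section 3.1.1 includes both perforated and non-perforated cases. Section 3.3 lists neither length of stay, operation and discharge dates, nor perforation status, and Section 4 plans no adjustment for any of them.

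The time at which the productivity survey is sent also varies. It is 10 days after discharge in the text of Section 3 and in most of Section 5.3, 10 days post-operative in the Section 3 schedule tables, and one week after discharge in one sentence of Section 5.3.

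**The concern.** Discharge is not a fixed point in recovery. Take a parent who misses work on the second day after surgery. With a discharge start, those hours count if the child is already home and do not count if the child is still in hospital, although the loss is the same.

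The design compares an earlier phase with a later one, about six months each, so anything that changes stay over calendar time falls between the groups. Section 1.1 describes a general move to earlier discharge: "In the context of transitioning to same-day or early post-operative discharges, parents are facing the responsibility". The tool could also act on stay itself, since Section 1.1 links child anxiety to later discharge. In either case a shorter stay in the post-implementation phase would move hours from uncounted hospital days to counted home days, and the tool would tend to look worse with total loss unchanged. The variables listed in Section 3.3 would neither reveal the shift nor allow a correction.

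Even with equal stays, a discharge start leaves in-hospital hours out of a study whose own question is about the post-operative period.

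**Working it through.** **Which start applies.** Every passage that gives a time starts at discharge, and Sections 1.1 and 2.1 give it as the specific meaning of the post-operative (recovery) period. Section 4 uses the same term, "due to caring for a child in the post-operative recovery period", without a time. A discharge start is therefore a natural reading of Section 4, but Section 4 does not state it and can also be read as starting at operation.

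**Plan's own figure.** Section 3.2 gives 100 per phase. No effect size, SD or power supports it, so it cannot be reproduced. For scale, at two-sided 0.05 and 80% power the detectable difference is (1.96 + 0.84) × √(2/100) = 0.40 SD.

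**Inputs for the shift.**
- From the documents: 100 per phase (Section 3.2); significance at 0.05 (Section 4; sidedness not stated, taken as two-sided); 25-30% perforated (Section 1.1.1).
- Assumed: SD of hours missed 24, with 16 and 32 as a range; hours missed per hospital day from 40/7 = 5.7 (a 40-hour week spread over calendar days) to 8 (every hospital day a full working day, an upper figure); mean stay shorter by 0.1, 0.25 or 0.5 day in the post-implementation phase; no true effect on total hours.

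**Formulas.** Shift = hours per day × change in mean stay. SE = SD × √(2/100), which is 24 × 0.1414 = 3.39 h at SD 24. Two-sided false-positive rate = P(|Z + shift/SE| > 1.96).

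| Fall in mean stay | Shift at 5.7 h/day | Rate, SD 24 | Shift at 8 h/day | Rate, SD 24 |
|---|---|---|---|---|
| 0.1 day | 0.6 h | 5.3% | 0.8 h | 5.6% |
| 0.25 day | 1.4 h | 7.1% | 2.0 h | 9.1% |
| 0.5 day | 2.9 h | 13.4% | 4.0 h | 21.8% |

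At 8 h per day the three rates are 6.4%, 14.3% and 42.4% with SD 16, and 5.4%, 7.3% and 14.3% with SD 32.

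These are totals over both directions. At SD 24 and 8 h per day, the rate in the direction that makes the tool look harmful is 4.2% for 0.1 day and 8.5% for 0.25 day.

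**Perforation mix.** Assume a 1-day stay for simple cases and 4 to 6 days for perforated cases. Moving the perforated share from 25% to 30% changes mean stay by 0.05 × (4 − 1) = 0.15 to 0.05 × (6 − 1) = 0.25 day. That is 0.9-1.4 h at 5.7 h per day, or 1.2-2.0 h at 8 h per day, which is small.

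**Counting from surgery.** With 7 days of care from operation at 5.7 h per day, the total is 40.0 h whatever the stay. Counted from discharge, the same family contributes 5.7 × (7 − 2) = 28.6 h with a 2-day stay and 5.7 × (7 − 1) = 34.3 h with a 1-day stay. A surgical start removes the shift.

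**The case against.** A reader might infer that the plan counts hours only from discharge and so definitely drops admission hours. The documents do not establish that. Section 4 has no discharge anchor, and the questionnaire, which Section 3 says is attached, is not in the documents, so the recall period put to caregivers cannot be checked. This part of the objection stands: the defect is an inconsistent start, with a bias that follows under one reading.

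A reader might also infer that any change in stay moves hours. It does not if no work is missed on the affected days. Nor does it if the absence fills a window of fixed length after discharge, because the end of that window moves with its start. This also stands.

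No change in stay between phases is predicted. The remark on earlier discharge is general background, and Section 5.2 says the study leaves current practice guidelines for appendicitis unchanged. Simple cases already go home the same or next day, so there is little room for a fall. If only the 25-30% perforated cases changed, a 0.5-day fall in the overall mean would need their stay to fall by 0.5/0.30 = 1.7 to 0.5/0.25 = 2.0 days. This limits the likely size but does not remove the mechanism.

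Finally, home-care burden after discharge is a coherent target, and Section 1.1 motivates it. That is a reason to keep post-discharge hours as an outcome. It does not settle which start the primary outcome has, and the study question asks about the post-operative period.

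**Conclusion.** The start of the primary outcome is worded inconsistently and should be fixed. If discharge is used, in-hospital hours are left out, mainly for perforated appendicitis, and a difference in stay or perforation mix between the sequential phases can bias the comparison, with no listed data to correct it.

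The size is conditional. It rests on an assumed SD, assumed hours missed per day and an assumed change in stay, none of which the documents give. At SD 24, a fall of 0.25 day takes the two-sided false-positive rate from 5% to about 7-9%, and 0.5 day takes it to about 13-22%. A 0.1-day fall, or a move in perforated share within the protocol's own range, matters little. For elective hernia repair the documents give no stay, so nothing can be said about its size there.

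The documents do not support the further claim that perforated families have their largest loss left out; no hours are given for either setting. This is a cheap improvement to make before the questionnaire is final, not evidence that the comparison will be biased.

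**What to change.** 1. Reconcile the survey timing first: 10 days after discharge, 10 days post-operative and one week after discharge cannot all hold. Under the one-week version, a child discharged on the day of surgery would be surveyed on day 7.
2. In Sections 1.1, 2.1, 2.2 and 4, define the primary outcome as hours of paid or unpaid work missed from the day of surgery to one fixed post-operative day that has passed for every family when the survey is sent.
3. In the questionnaire, ask for hours missed while the child was in hospital and hours missed after discharge as two entries. Keep post-discharge hours as a secondary outcome.
4. Add length of stay and perforation status to Section 3.3, and use perforation status for adjustment or stratification in Section 4. Because Section 5.3 says answers will not be linked to emails, the simplest route is to ask for both in the survey itself.

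The cost is outcome wording and a few questionnaire items, at a point when the pilot phase is due to adapt the questionnaire anyway. Families with long stays face slightly longer recall, and home-care hours beyond the fixed day appear only in the secondary outcome.

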### 2.3 Study Question

Does the implementation of an education tool for patients and caregivers decrease preoperative parental anxiety and caregiver productivity loss in the post-operative period in the realm of pediatric surgery?

## 3 STUDY METHODS

This study is a collaboration between the Harvey E. Beardmore Division of Pediatric Surgery and the Patient Education Office, with whom we have developed a plain-language patient education tool for appendectomies.

This study has several phases, which will be similar for all three surgical procedures. For convenience, the phases have been described in relation to the first surgical procedure that will be examined, namely appendectomy:

This study has several phases:

#### 1. Pilot Phase (2-3 weeks) – Validation of Questionnaire

- A convenience sample of 5 patients with acute appendicitis and their families will be selected during their routine postoperative visits to provide input on the questionnaire. The preliminary questionnaire is attached, and was developed by the authors based on the Amsterdam Preoperative Anxiety and Information Scale (APAIS), Productivity and Disease Questionnaire (PRODISQ), the Health and Labor Questionnaire (HLQ), and a literature review.
- A convenience sample of 5 surgeons and 5 nurses will also be solicited to provide feedback.
- The questionnaire will be adapted based on qualitative feedback from the participants listed above.

2. Pre-Implementation Phase (100 patient/approx. 6 months)

- All patients with acute appendicitis who undergo appendectomies will be eligible to participate, and families will be consented prior to surgery. The parental anxiety assessment will be done only before surgery with the Amsterdam Preoperative Anxiety and Information Scale (APAIS). In addition, the email of one of the primary caregivers will be collected, and the caregiver will receive an email with a link to the post-operative questionnaire 10 days post-discharge. At 14 days post-discharge, they will receive a reminder email with the link to the questionnaire. All responses to the questionnaire are voluntary and anonymous.

Before Surgery	Obtain Consent
	Amsterdam Preoperative Anxiety and Information Scale (APAIS)
	Collection of email of primary caregiver
10 days Post-operative	Link to Parental Productivity Survey will be sent
14 days Post-discharge	Reminder email with link to the questionnaire will be sent.

3. Post-Implementation Phase (100 patient/approx. 6 months)

- The education tool will be distributed to families whose child is undergoing an appendectomy. The parental anxiety assessment will be done in the same way as above, only before surgery with the Amsterdam Preoperative Anxiety and Information Scale (APAIS). In addition, the email of one of the primary caregivers will be collected, and the caregiver will receive an email with a link to the post-operative questionnaire 10 days post-discharge. At 14 days post-discharge, they will receive a reminder email with the link to the questionnaire. All responses to the questionnaire are voluntary and anonymous.

Before Surgery	Obtain Consent
	Amsterdam Preoperative Anxiety and Information Scale (APAIS)
	Collection of email of primary caregiver
10 days Post-operative	Link to Parental Productivity Survey will be sent & Link to Patient Education Tool Survey will be sent
14 days Post-discharge	Reminder email with links to the questionnaires will be sent.

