### 3.3 Description of data being retrieved

For each patient, we plan to collect answers from the circulated questionnaires, which will include questions related to the child and caregiver. This survey will not collect any identifiable information. However, we will collect some patient/parent information including:

- Age of the child and caregiver
- Relation of the caregiver to the child
- Caregiver's education level
- Caregiver's yearly income
- Caregiver's work hours

To assess indirect resource use (productivity losses) we will collect the following information:

- Hours absence from paid or unpaid job
- Loss of leisure time and sleep
- Access to compensated or uncompensated help at home
- Number of follow ups with medical personnel during the child's recovery
- Utility of education tool

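### In the post phase the tool survey is sent alongside the productivity survey in no set order, so the self-reported primary outcome is collected beside an evaluation of the intervention in one group only

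*Combined protocol and SAP*

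**What the plan says.** Section 3 (Study Methods) gives one contact schedule per phase.

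- **Pre-Implementation Phase:** the day-10 row reads "Link to Parental Productivity Survey will be sent". The day-14 row reads "Reminder email with link to the questionnaire will be sent".
- **Post-Implementation Phase:** the day-10 row repeats the pre-phase entry and adds "Link to Patient Education Tool Survey will be sent". The day-14 row reads "Reminder email with links to the questionnaires will be sent".

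The post-phase narrative above its table speaks, as in the pre phase, of a single post-operative questionnaire. Section 5.3 allows for one or more questionnaires at day 10. Section 3 states that responses are voluntary and anonymous.

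Section 4 (Data Analysis) defines the primary outcome as "loss of parental productivity measured in hours of paid or unpaid work missed due to caring for a child", compared between caregivers who did and did not receive the tool. Section 3.3 gives the source of the data: "we plan to collect answers from the circulated questionnaires, which will include questions related to the child and caregiver".

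**The concern.** Hours missed are recalled and reported by the caregiver, and returning the form is optional. Such an outcome can be affected by what is asked next to it and by how long the whole task looks. Only post-phase caregivers are asked, alongside their hours, for their views on the tool. Some may open that survey first, and all of them face two surveys instead of one.

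Two things could follow in the post phase only: the answers could be cued by the evaluation, or the extra survey could change who responds. Either difference coincides exactly with the tool versus no-tool comparison. Section 3 says the phases will be similar for all three procedures, so the asymmetry would recur for appendectomy, umbilical hernia and inguinal hernia.

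**Working it through.** **Step 1. Set the two schedules side by side.**

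| Feature | Pre phase | Post phase |
|---|---|---|
| Name of the outcome survey | Parental Productivity Survey | Same |
| Route | E-mailed link | Same |
| Timing | Day 10, reminder at day 14 | Same |
| Companion survey at day 10 | None | Patient Education Tool Survey |
| Day-14 reminder | One link | Both links |
| Order of the two surveys | Not applicable | Not stated |

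The tables count day 10 from the operation and the text counts it from discharge. That inconsistency is the same in both phases and has no bearing here. The only difference between phases is the companion survey.

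**Step 2. Look for a safeguard.** No section fixes the order, makes the tool survey conditional on returning the productivity survey, or plans to compare response between phases. Section 4 plans bivariate tests and describes no adjustment. Section 3.3 lists "Utility of education tool" among the productivity-loss items without saying which form carries it.

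**Step 3. Can analysis separate it?** Cueing cannot be separated, because every post-phase caregiver is sent the companion survey and no pre-phase caregiver is. Response can be partly examined. Return rates by phase need only links sent and surveys returned, and Section 3.3 collects caregiver age, relation to the child, education, income and work hours.

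**Step 4. Illustrate the scale.** The plan gives no mean, SD, effect size, power or response rate, so there is no figure to reproduce. The inputs are:

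- n = 100 per phase (Section 3.2) and alpha 0.05 (Section 4), taken as two-sided because the plan does not say.
- A true effect of zero and a pure reporting shift δ in SD units, both assumed.
- n = 60 responders per phase as an alternative, also assumed.

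SE = √(2/n), which is 0.141 at n = 100 and 0.183 at n = 60.

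Rejection rate = Φ(δ/SE − 1.96) + Φ(−δ/SE − 1.96).

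For δ = 0.1 and n = 100: δ/SE = 0.707, so the rate is Φ(−1.253) + Φ(−2.667) = 0.105 + 0.004 = 0.109.

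| Assumed shift (SD) | n = 100 per phase | n = 60 per phase |
|---|---|---|
| 0 | 5.0% | 5.0% |
| 0.05 | 6.4% | 5.9% |
| 0.1 | 10.9% | 8.5% |
| 0.2 | 29.3% | 19.5% |
| 0.3 | 56.4% | 37.6% |

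For comparison, the difference detectable with 80% power at 100 per phase is (1.960 + 0.842) × 0.141 = 0.40 SD. The documents give no basis for choosing any row of the table.

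**The case against.** The strongest case against is that the extra cue may be negligible. Post-phase families have already been given the tool and have consented before surgery, so they know they received it within a study. Hours missed is a quantity, not a rating, so a wish to please is less obviously at work. The tool survey's content is not in the text available, so its length cannot be judged. A survey about the tool also cannot sensibly go to caregivers who never had it. All of this stands. It limits the weight of the point and places the weakness in joint, unordered sending, not in the absence of the tool survey from the pre phase.

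A reader might also infer more than the documents support:

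- **That the survey lowers reported hours and so favours the tool.** Nothing in the documents gives a direction.
- **That anonymity is what makes the bias irremovable.** Linking answers to e-mail addresses would not remove cueing either, and response and responder mix can be compared by phase without linkage.
- **That one e-mail carries both links at day 10.** This is an inference from a shared table row. Only the reminder is clearly one message with several links.
- **That the tool survey is merely descriptive and can be lost freely.** No section says so, and Section 6 intends the results to improve the educational materials.

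**Conclusion.** The point holds in a limited form. The schedules differ as shown, and no section orders the surveys or delays the tool survey. The primary outcome is self-reported and voluntary, so an effect on answers or on response in the post phase is plausible and would be confounded with the tool effect.

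Whether it occurs, in which direction and how large it is cannot be determined from the documents. The rejection rates above rest on assumed shifts, a two-sided test and the normal approximation, and they are not estimates. The issue is minor beside the unblinded, non-randomised before-after comparison, which the fix leaves untouched. It is worth correcting because it is an avoidable difference between phases and costs little to remove.

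**What to change.** 1. Use the same productivity-survey e-mail and the same day-14 reminder in both phases, each with the productivity link only.
2. Show the Patient Education Tool Survey only after the productivity survey has been submitted, or send it in a separate e-mail after the day-14 reminder.
3. State which form carries the item on the tool's usefulness listed in Section 3.3. If it is in the productivity survey, move it to the tool survey.
4. Report productivity-survey response rates and the Section 3.3 responder characteristics by phase.

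The cost is a survey-software setting or one extra mailing, an edit to two rows of the post-phase table, and a short addition to Section 4. The downside is possibly somewhat fewer tool-survey responses. These are not among the primary or secondary outcomes in Section 4, though the study does mean to use them. If that loss matters, the later separate e-mail is the better option, because it also reaches caregivers who did not return the productivity survey.
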